5.1.3 ADDITIONAL CLINICAL OUTCOMES

- Discharge status
- Rehospitalization within 30 days after discharge
- Vital status 30 days after discharge

Etiology of clinical failure is also assessed:

- Minimum inhibitory concentrations (MIC) of antibacterial drugs
 - Day of assessment since index hospitalization
 - MIC of ceftaroline for all isolated pathogens

PFIZER CONFIDENTIAL

CCI

- MIC of oxacillin, vancomycin, linezolid, and daptomycin for *S. aureus*
- MIC of ceftriaxone for MSSA
- MIC of penicillin and ceftriaxone for *S. pneumonia*

5.1.4 TREATMENT MODIFICATIONS / AE

The following variables are extracted from charts of eligible patients to assess proportion of patients who had treatment modification of Zinforo® treatment:

- Treatment switch to another IV antibiotic due to adverse event (AE)
- Drug-drug interaction
- Insufficient response
- Microbiological diagnosis

AEs resulting in treatment modification are also collected:

- Infections and infestations
- Blood and lymphatic system disorders
- Immune system disorders
- Nervous system disorders
- Vascular disorders
- Gastrointestinal disorders
- Hepatobiliary disorders
- Renal urinary disorders
- General disorders and administrative site conditions
- Investigations
- Other
- Seriousness of AE
- Type of criteria applied to assess seriousness of AE

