9.4. Data Sources

Data for this study will be collected by a retrospective medical chart extraction from participating sites. The sites will be hospitals in Europe and Latin America that have treated patients with CAP or cSSTI in usual care during the study period. Approximately 600 patient charts will be included in this study from approximately 35-40 sites in Europe and Latin America (15-20 charts per site). Each chart will be retrieved and screened against the inclusion and exclusion criteria. The sites will be responsible for performing all data extraction. For eligible patients, relevant data will be extracted from the hospital medical records from 3-months before the date of the index hospital admission until 30-days after the hospital discharge date or death, whichever occurs first. All data will be entered by sites into electronic case report forms (eCRFs). De-identified data will be collected following the Health Insurance Portability and Accountability Act (HIPAA)-compliant safe harbor approach.³⁴

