11. MANAGEMENT AND REPORTING OF ADVERSE EVENTS/ADVERSE REACTIONS

This study protocol requires human review of patient-level unstructured data; unstructured data refer to verbatim medical data, including text-based descriptions and visual depictions of medical information, such as medical records, images of physician notes, neurological scans, X-rays, or narrative fields in a database. The reviewer is obligated to report adverse events (AEs) with explicit attribution to any Pfizer drug that appear in the reviewed information (defined per the patient population and study period specified in the protocol). Explicit attribution is not inferred by a temporal relationship between drug administration and an AE,

but must be based on a definite statement of causality by a healthcare provider linking drug administration to the AE.

The requirements for reporting safety events on the non-interventional study (NIS) adverse event monitoring (AEM) Report Form to Pfizer Safety are as follows:

- All serious and non-serious AEs with explicit attribution to **any Pfizer drug** that appear in the reviewed information must be recorded on the CRF and reported, within 24 hours of awareness, to Pfizer Safety using the NIS AEM Report Form.
- Scenarios involving drug exposure, including exposure during pregnancy, exposure during breast feeding, medication error, overdose, misuse, extravasation, lack of efficacy, and occupational exposure associated with the use of a Pfizer product must be reported, within 24 hours of awareness, to Pfizer Safety using the NIS AEM Report Form.

For these AEs with an explicit attribution or scenarios involving exposure to a Pfizer product, the safety information identified in the unstructured data reviewed is captured in the Event Narrative section of the report form, and constitutes all clinical information known regarding these AEs. No follow-up on related AEs will be conducted.

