8.1.7 TREATMENT MODIFICATIONS / ADVERSE EVENTS IN PATIENTS WITH CAP

Table 24. Clinical failure with Zinforo in patients with CAP

Clinical failure with Zinforo	All CAP patients (N=XX)	
	n	%
Etiology of clinical failure		
Failure related to CAP		
Failure unrelated to CAP		
Unknown		
Reason for clinical failure		
Treatment modification due to AE		
Time to modification (days)		
Mean (SD)		
Median (Min-Max)		
Unknown		
Drug-drug interaction		
Insufficient response		
Death due to index infection		
Time to death due to infection (days)		
Mean (SD)		
Median (Min-Max)		
Unknown		
Death due to other		
Relapse or recurrence		
Time to relapse/recurrence:		
Mean (SD)		
Median (Min-Max)		
Unknown		

Abbreviations: AE: adverse events; Max: maximum; Min: minimum; SD: standard deviation.

PFIZER CONFIDENTIAL

CCI

Table 25. Clinical failure with Zinforo due to adverse events in patients with CAP

Clinical failure to Zinforo due to AEs	All CAP patients (N=XX)
	n %
AE causing Zinforo discontinuation	
Infections and infestations	
Clostridium difficile colitis	
Other	
Blood and lymphatic system disorders	
Activated partial thromboplastin time (aPTT) prolonged	
Agranulocytosis	
Anaemia	
Eosinophilia	
International normalized ratio (INR) increased	
Leucopenia	
Neutropenia	
Prothrombin time (PT) prolonged	
Thrombocytopenia	
Other	
Immune system disorders	
Anaphylaxis	
Hypersensitivity (e.g. urticarial, lip and face swelling)	
Pruritus	
Rash	
Other	
Nervous system disorders	
Dizziness	
Headache	
Other	
Vascular disorders	
Phlebitis	
Other	
Gastrointestinal disorders	
Abdominal pain	
Diarrhea	
Nausea	
Vomiting	
Other	
Hepatobiliary disorders	
Increased transaminases	
Other	
Renal urinary disorders	
Blood creatinine increased	
Other	
General disorders and administrative site conditions	
Infusion site reaction (e.g. erythema, phlebitis, pain)	
Pyrexia	
Other	
Investigations	

PFIZER CONFIDENTIAL

CCI

Clinical failure to Zinforo due to AEs	All CAP patients (N=XX)	
	n	%
Coombs direct test positive		
Other		
Unknown		

Abbreviations: AE: adverse events, aPTT: activated partial thromboplastin time

PFIZER CONFIDENTIAL

CCI

Table 26. Seriousness of adverse events in patients with CAP

Clinical failure to Zinforo	All CAP patients (N=XX)	
	n	%
Serious AE at Zinforo discontinuation		
Yes		
No		
Unknown		
Seriousness criteria applied (for AEs indicated as serious)		
Resulted in death		
Life-threatening		
Hospitalization/prolongation of hospitalization		

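### The protocol puts every explicitly drug-attributed adverse event on the CRF, but the SAP summarises only those that led to modification or discontinuation of Zinforo

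*SAP*

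**What the plan says.** **Collection.** Protocol section 11 covers "All serious and non-serious AEs with explicit attribution to" any sponsor drug, and says that those "that appear in the reviewed information must be recorded on the CRF and reported, within 24 hours of awareness, to Pfizer Safety". Attribution cannot be inferred from timing; it "must be based on a definite statement of causality by a healthcare provider linking drug administration to the AE". Nothing in that section limits the rule to events that changed treatment. Protocol section 9.4 sets the end of chart extraction: "until 30-days after the hospital discharge date or death, whichever occurs first".

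**Analysis.** SAP section 5.1.4 says "AEs resulting in treatment modification are also collected" and then lists the AE categories. SAP section 4.1.2 declares a safety analysis set inapplicable. In SAP section 8.1.7, Table 25 lists AEs under a heading confined to those that caused Zinforo to be stopped. Table 26 is titled "Seriousness of adverse events in patients with CAP", with all CAP patients as the denominator; its row label is "Serious AE at Zinforo discontinuation". Tables 52 and 53 in section 8.1.14 repeat this for cSSTI.

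Table numbers here follow the shells in SAP section 8. The list of tables at the front of the SAP numbers the two cSSTI AE tables 54 and 55.

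**The concern.** The protocol asks sites to put one set of AEs on the CRF, and the SAP reports a smaller one without saying that it does so or why. Two kinds of attributed event drop out. One is a reaction, possibly serious, that clinicians managed while continuing the drug. The other is a reaction that appeared after the last dose but within the extraction window. *C. difficile* colitis shows the problem well: it has a row in Tables 25 and 52, but only as a cause of stopping Zinforo.

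At stake is what the report can say about tolerability. The background sections of both documents name tolerability as part of the need for another treatment option, so readers will look for it in the results. A discontinuation-only count, under a short title that speaks of the seriousness of AEs in general, is easily quoted as the whole picture.

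**Working it through.** The plan states no figure on this point to reproduce, and the study is descriptive with no alpha or power. The check is therefore a comparison of the texts, followed by an illustration of size.

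**Step 1: what should be on the CRF.** From Protocol sections 11 and 9.4: every AE with an explicit causal statement naming a sponsor drug, of any seriousness, in records up to 30 days after discharge or to death.

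**Step 2: what the AE shells accept.** From SAP section 5.1.4 and Tables 25, 26, 52 and 53: AEs that led to modification (text) or discontinuation (shells). An AE that began after the last dose cannot have caused discontinuation. An AE treated through did not. Both satisfy step 1 and fail step 2.

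**Step 3: whether another shell picks them up.**

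| Shells (CAP / cSSTI) | Nearest content | Why it does not fill the gap |
|---|---|---|
| 24 / 51 | Reasons for clinical failure | An AE counts only as the cause of a modification |
| 27 / 54 | Side effect as a reason for the next antibiotic | Requires a switch |
| 28 / 55 | AE during the post-Zinforo antibiotic | Concerns the later drug, and requires a modification |
| 16 / 43 | Reason for readmission | Index infection, other or unknown; no AE category |
| 14 / 41 | Renal replacement, sepsis, septic shock | No drug attribution |
| 23 / 50 | In-hospital death, vital status | No drug attribution |

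No shell in either cohort shows attributed AEs in patients who completed Zinforo, or attributed AEs that began after it ended.

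**Step 4: the two terms differ.** Protocol section 8 defines modification as a change to a different intravenous antibiotic for listed reasons. Stopping for an AE without such a change is a discontinuation but not a modification. SAP section 5.1.4 and the shells therefore do not describe exactly the same events.

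**Step 5: possible size, illustration only.** Protocol section 7 quotes 2% of patients discontinuing because of AEs in each of two US registry sub-studies. The target is about 600 patients. Tables 25 and 52 together would then show 0.02 × 600 = 12 patients. The rate r of any explicitly attributed AE is not in the documents and is assumed below. I also assume that all 12 are among the attributed cases, so the number in no AE table is 600r − 12.

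| Assumed r | Patients with an attributed AE | In no AE table | Share |
|---|---|---|---|
| 3% | 18 | 18 − 12 = 6 | 6/18 = 33% |
| 5% | 30 | 30 − 12 = 18 | 18/30 = 60% |
| 10% | 60 | 60 − 12 = 48 | 48/60 = 80% |
| 20% | 120 | 120 − 12 = 108 | 108/120 = 90% |

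The spread shows that the documents do not fix the size.

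**The case against.** The strongest reply is that the SAP follows the objectives. None of them is a general safety objective. The only AE-related one is the proportion with treatment modification, and the variable list in Protocol section 9.3 names AEs only as a cause of modification. Protocol section 11 governs reporting to the sponsor and promises no AE summary. Discontinuation because of AEs is also the measure quoted from the US registry, so the planned tables give a like-for-like comparison.

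Much of this stands, and it limits the importance of the point. It does not settle it. Section 11 requires the CRF as well as the safety form, so the mismatch also lies inside the protocol, between 9.3 and 11. Protocol section 9.7 lets the SAP modify the plan, but the SAP does not say that it leaves these events out. The comparison with the registry survives if the discontinuation column is kept.

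A second reply is that the data may not exist in usable form. The eCRF is not among the documents, and the only AE fields described are tied to modification. That is fair: a reader might infer from section 11 that these AEs are already in the database, but the documents state a requirement and do not confirm a field.

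A third reply is that Tables 26 and 53 print their restriction in the row label. That is true. A reader might take the title to mean that the SAP plans an overall serious AE proportion and understates it. It plans no such figure, and the defect there is a title broader than its content.

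**Conclusion.** The point holds as a gap between required collection and planned reporting. Explicitly attributed AEs that were treated through, or that began after the last dose, appear in no planned study result. It should be corrected, but it does not touch the estimates of clinical response.

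The number affected is unknown. A reader might infer that most AEs are missed because most of the observation time follows the last dose: with the stated treatment durations and 30 days after the last dose, 30/(30 + d) is 86% for d = 5 days, 81% for d = 7 and 68% for d = 14. The documents do not support that reading. This is a share of calendar time, not of events; nothing shows that attributed AEs arise or are charted evenly over it. Extraction also stops at death, and Tables 19 and 46 allow for Zinforo given at home or in an outpatient setting, so treatment need not end by discharge.

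Nor are these events lost altogether, since section 11 sends them to sponsor safety within 24 hours of awareness. What is missing is their place in the results.

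The conclusion rests on section 11 applying as written and on the SAP shells being the full set of planned tables.

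**What to change.** 1. In Tables 25, 26, 52 and 53, add a column for any AE explicitly attributed to Zinforo beside the existing one for AEs that led to discontinuation. Give seriousness and a per-patient count for both.
2. Separate Zinforo from other sponsor drugs, because section 11 covers them all.
3. Before finalising the shells, confirm that the eCRF holds these AEs. If it does not, reconcile Protocol sections 9.3 and 11.
4. Use one term, modification or discontinuation, in SAP section 5.1.4 and the shells, or define both.
5. Retitle Tables 26 and 53 so that the discontinuation-only figure cannot be taken for an overall serious AE proportion.
6. State in the SAP and the report that the new counts depend on explicit causal statements in charts, and so are minimum counts and not incidence rates.

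The cost is one column in four shells and some programming, with no new chart review if the CRF already holds the events. If it does not, the cost is higher: an eCRF change and renewed extraction. The reported AE count will rise.

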5.1.5 OTHER ENDPOINTS

Beyond the range of effectiveness endpoints specified above (sections 5.1.1), the additional outcomes listed below will be analysed.

5.1.6 PATIENT CHARACERISTICS AT INDEX HOSPITALIZATION

The following variables on patient characteristics are collected from the patient charts:

- Patient demographics at index hospitalization
 - Year of patient hospitalization
 - Sex
 - Age category: >65 and ≤ 65 years
 - Country
 - Race, ethnicity

PFIZER CONFIDENTIAL

CCI

- Height (cm)
 - Weight (kg)
 - Patient's type of residence/cohabitation
 - Smoking habits
- Medical history of patients treated with Zinforo®
 - Medical conditions that the patient presented with at index visit hospitalization
 - Hospitalization for any reason in the 3 months before the index visit
 - Invasive major surgical treatment in the 3 months before the index visit hospitalization
 - Therapies in the 3 months before the index visit hospitalization
 - Antimicrobial (e.g. antibiotics, antivirals)
 - Immunosuppressors/ immunomodulators
 - Anticoagulants
 - Non-steroid anti-inflammatory agents (NSAIs)
 - Home infusion therapy
 - Home wound care provided by a medical professional
- CAP-specific characteristics
 - Radiographic findings
 - Triggering signs and symptoms at diagnosis
 - Severity of CAP
 - Prognostic Scoring system
 - Time of CAP diagnosis
 - Recurrence of infection
 - Microbiologic diagnosis / type of investigation performed
 - PCF determination of H1N1 influence virus
 - Influenca vaccination status (12 month pre index)
 - Pneumococcal vaccination status
 - Biomarkers used for monitoring
- cSSTI-specific characteristics
 - Type of lesion involved
 - Type of body area involved
 - Extension of the skin infection in (sqcm)
 - Level of infection
 - Anatomical structures that were affected
 - Time of c SSTI diagnose
 - Recurrence of infection?
 - Triggering signs and symptoms at diagnosis
 - Systemic signs of cSSTI diagnosis
 - Diagnostic tests performed

PFIZER CONFIDENTIAL

CCI

- Microbiological diagnosis
- Methicillin susceptible S. aureus (MSSA)

5.1.7 PHYSICIANS' USE OF ZINFORO® DURING INDEX HOSPITALIZATION

- Pre Zinforo® treatment
 - Antibiotic class
 - Line of therapy
 - Route of administration
 - Duration of treatment Time from admission to 1st dose
 - Time from symptom onset to 1st dose
 - Treatment type
 - Daily dose
 - Treatment modified (Reason)
 - Treatment response/ failure
 - Time to clinical response / failure
 - Clinical failure details
- Zinforo® treatment
 - Duration of treatment
 - Time from admission to 1st dose
 - Time from symptom onset to 1st dose
 - Treatment type
 - Daily dose
 - Number of infusions per day
 - Administration location
 - Zinforo® as monotherapy/ combination (including further details of combination therapy)
 - Concomitant therapy
- Post Zinforo® antibiotic treatment
 - Generic name of treatment
 - Line of therapy
 - Route of administration
 - Time from Zinforo® discontinuation to initiation of new treatment
 - Daily dose
 - Number of doses administered
 - Administration location
 - Reason for switch to this treatment:
 - Treatment response
 - Clinical cure achieved?
 - Clinical failure details

5.1.8 HEALTHCARE RESOURCE USE AND COST FOR PATIENTS STARTING ZINFORO®

The following variables are collected in the CRF on the resource utilization for patients starting Zinforo® during index hospitalization:

- Duration of index hospitalization
- Duration in intensive care unit during index hospitalization
- Renal replacement therapy initiated after initiating Zinforo®
- Treatments (Surgery / blood pressure support) during index hospitalization
- Home-based care through a health-care agency (e.g. for wounds, intravenous infusions), nursing services, etc. after discharge (days)
- Re-hospitalization within 30 days of initial discharge:
 - Number of times and days
 - Reason: Index infection, other
- Development of sepsis during index hospitalization
 - Sepsis
 - Severe sepsis
 - Septic shock
- Patient treatment during index hospitalization
 - Quick sepsis-related organ failure assessment (qSOFA) conducted at the time of the index hospitalization admission:
 - Patient requiring isolation
 - Patient requiring mechanical ventilation
 - Patient requiring oxygen therapy
 - Patient requiring parenteral nutrition
 - Patient suffer acute renal failure necessitating renal replacement therapy during index
 - Patient receiving during index therapy surgery or blood pressure support
- Total doses of Zinforo®
- Total dose of other antibiotics in combination therapy with Zinforo®
- Total doses of other antibiotics post Zinforo® treatment

To get an indication for the economic impact related to the treatment of CAP and cSSTI approximate hospitalization cost will be calculated based on the calculated sum of hospital days and a list of country specific per diem rates. To assess a range of the cost and depending on the data available from each of the countries two per diem rates will be used for the cost calculation: The average per diem rate of hospitals providing standard services for these type of infections and average per diem rate of hospitals providing the highest level of medical services. “Standard” or secondary level hospitals are anticipated to be institutions that are primarily treating referral cases, with bed size ranging from 200

PFIZER CONFIDENTIAL

CCI

to 800 beds. Advanced or tertiary-level/teaching hospitals will be typically comprise hospitals intended for referral cases, with a teaching component and highly specialised staff and technical equipment, including ICU and bed size ranging from 300 to 1,500 beds. The cost estimates will be expressed in both national currency as well as in USD using sector specific exchange rate or power purchasing parities:

- Country specific calculation of approximate hospitalization cost:
 - Cost assuming a standard level hospital
Total hospital cost= total number of bed days * per diem rate standard hospital (local currency / USD)
 - Cost of advanced level hospitals
Total hospital cost= total number of bed days * per diem rate advanced hospital (local currency / USD)

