	
assessment score at admission);
 
• Disease Characteristics for CAP (time from diagnosis to Zinforo initiation, diagnostic criteria met, imaging findings suggestive of bacterial pneumonia, signs of acute illness at diagnosis);• Disease characteristics for cSSTI (time from diagnosis to initiation of Zinforo diagnostic criteria met, cellulitis/fasciitis, abscess, post-traumatic wound, post-surgical wound, diabetic leg ulcer, peripheral vascular disease ulcer, lesion size, lower extremities affected, swelling/induration, skin necrosis, recurrent skin infection episode, nosocomial infection);• Hospitalization Information (duration of hospitalization, discharge destination, discharge status, ICU duration, ICU discharge date);• Microbiological Diagnosis (investigations or diagnostic tests performed, positive microbiological diagnosis obtained, microorganism name, bacteremia diagnosed);• Zinforo® Treatment (treatment duration, line of therapy, time from hospital admission to first dose, empiric vs. definitive therapy, monotherapy vs. combination therapy, daily dose, number of doses administered, treatment duration, clinical response, clinical response definition (Halm criteria, switch to oral antibiotic, other) time to clinical response (days), treatment streamlining/de-escalation, treatment modification, time to treatment modification (days), reason for treatment modification, ICU vs. general medical ward administration);• All Other Antibiotic Treatments during the index hospital admission (each monotherapy/combination antibiotic therapy name, line of therapy, route of administration, duration of treatment, number of doses administered, treatment response, time to treatment modification from initial dose (days), reason for treatment modification, ICU vs. general medical ward administration);• Clinical Outcomes and Healthcare Resource Use after first Zinforo® dose (number of days in the hospital, switch to another IV antibiotic, switch to an oral antibiotic, time to first oral antibiotic dose, admission to ICU, time in ICU,
--	---

	mechanical ventilation, surgery, reinfection or recurrence, acute renal failure, length of acute renal failure, blood pressure support, fluid resuscitation, vasopressors, septic shock, isolation required, parenteral nutrition, length of parenteral nutrition, home-based care after discharge, in-hospital mortality, 30-day mortality, 30-day readmission after discharge).

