Data sources	Data will be retrospectively extracted from the hospital medical records of eligible patients. De-identified data will be collected following the Health Insurance Portability and Accountability Act (HIPAA)-compliant safe harbor approach. ³⁴
Study size	The target sample for recruitment is approximately 600 patients across all sites. The number of eligible CAP and cSSTI patients that each site will provide will vary depending on the historical usage of Zinforo® at that site up to 31-May-2019.
Data analyses	
The objective of this retrospective chart review study is descriptive in nature; therefore, no hypothesis testing will be performed. The results of the total study sample will be summarized using descriptive statistics. Data will be summarized by means, standard deviations (SD), medians, minimums and maximums for continuous variables; and by numbers and percentages for categorical variables. All summarized data will be presented in aggregate, and may be stratified by covariates of interest if a subgroup has a minimum sample size of 30 patients (5% of total study size).
 
Clinical outcomes and resource use following the initiation of Zinforo® treatment will be assessed according to patients' observed clinical response time (<72-hours, >72-hours, no response). The mean (SD) and median times to an outcome of interest (eg, length of stay in the hospital measured in days) will be calculated in each patient subgroup.

Milestones	
Completion of feasibility assessment: 15 September 2019.
 
Start of data collection: 01 December 2019.
 
End of data collection: 15 June 2020.
 
Final study report: 12 October 2020.

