8. RESEARCH QUESTION AND OBJECTIVES

Study Aim:

The overall study aim is to provide real world evidence (RWE) on the characteristics, clinical management, treatment outcomes and healthcare resource use of adult patients aged 18 years and older admitted to the hospital for CAP or cSSTI who received Zinforo[®] in a usual care setting in Europe and Latin America on or before 31-May-2019.

Specific Objectives:

- To describe the characteristics of patients hospitalized for CAP or cSSTI who received Zinforo® in a usual care setting in Europe and Latin America on or before 31-May-2019.
- To describe physicians' use of Zinforo® in the clinical management of patients hospitalized for CAP or cSSTI in relation to their use of other antibiotics (first-line vs. second-line/salvage, monotherapy vs. combination therapy, empiric vs. definitive therapy).
- To estimate the proportion of patients hospitalized for CAP or cSSTI who responded to Zinforo® (clinical response defined as no further intravenous (IV) antibiotic, switch to an oral antibiotic, or IV antibiotic treatment streamlining/de-escalation prior to discharge from the hospital).
- To estimate the proportion of patients hospitalized for CAP or cSSTI who had treatment modification of Zinforo® (defined as switch to another IV antibiotic due to an adverse reaction, drug-drug interaction, insufficient response, or a microbiological diagnosis indicating that the pathogen is not susceptible to Zinforo®).
- To describe the clinical outcomes (eg, hospital readmission, mortality) of patients hospitalized for CAP or cSSTI after starting Zinforo® stratified by clinical response.
- To describe the healthcare resource use of patients hospitalized for CAP or cSSTI after starting Zinforo® stratified by clinical response.

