- Zinforo® Treatment Response: Clinical response (response definition, treatment de-escalation, oral switch, time to symptom resolution, time to clinical stability (Halm criteria), time to oral switch). Clinical failure (treatment modification due to AE, DDI, or insufficient response, death due to index infection, death due to other. Relapse or recurrence. Time to relapse or recurrence).
- Healthcare Resource Use after date of first Zinforo® dose (number of days in the hospital, admission to ICU, time in ICU, surgery, mechanical ventilation, acute renal failure, length of acute renal failure, blood pressure support, fluid resuscitation, vasopressors, septic shock, isolation required, parenteral nutrition, length of parenteral nutrition, home-based care after discharge, in-hospital mortality, 30-day mortality, 30-day readmission after discharge, readmission for index infection, readmission for other reason).

Derived variables will be calculated from the reported values of other variables entered by sites. For example, type of CAP will be derived as follows:

Variable	Role	Data source(s)	Operational definition
Type of CAP	Effect modifier	Type of residence/co-habitation variable in Patient Demographics CRF.	CAP = Residence in private house or apartment only. HCAP =: residence in a nursing home, home care through a healthcare agency, previous admission to hospital with CAP (last 3 months), haemodialysis or chemotherapy for active cancer, with the exception of immunocompromised/immunosuppressed.

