7.1.3 STATISTICAL ANALYSES

7.1.4 SPECIFIC APPROACH

Using the endpoints described in section 5.1.6, patient characteristics will be described by summarizing patient demographics at index hospitalization, as well as patient's medical history. CAP-specific characteristics and cSSTI-specific characteristics will also be summarized for each patient cohort respectively. To describe physicians' use of Zinforo® in the clinical management of the patients hospitalized for CAP or cSSTI, details on pre-Zinforo treatment, Zinforo treatment as well as post-Zinforo antibiotic treatment will be summarized to describe line of therapy, monotherapy vs. combination therapy, etc (see related endpoints described in section 5.1.7). Proportion of patients with a clinical response, clinical cure and clinical failure in response to Zinforo® treatment will be summarized. Using the endpoints outlined in section 5.1.3, the clinical outcomes (e.g. hospital readmission, mortality) of patients hospitalized for CAP or cSSTI after starting Zinforo will be summarized and stratified by clinical response. Treatment modification Zinforo® and reasons for treatment modification will be described for the CAP and cSSTI patient cohorts, using the endpoints collected as described in section 5.1.4. Healthcare resource utilization will be described for patients hospitalized for CAP or cSSTI after starting Zinforo® and stratified by clinical response, using the appropriate endpoints as described in section 5.1.8.

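### Protocol 9.3 counts hospital and ICU days from the first Zinforo dose, but the SAP plans only whole-admission durations, so post-dose stay by response goes unreported

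*SAP*

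**What the plan says.** **Protocol.**
- Section 9.3 starts the clock explicitly: "Healthcare Resource Use after date of first Zinforo® dose (number of days in the hospital, admission to ICU, time in ICU, surgery". The Variables part of the abstract gives the same window: "Clinical Outcomes and Healthcare Resource Use after first Zinforo® dose (number of days in the hospital, switch to another IV antibiotic".
- The sixth objective in Section 8, repeated unchanged as Objective 6 in SAP 2.1.4, is "To describe the healthcare resource use of patients hospitalized for CAP or cSSTI after starting Zinforo® stratified by clinical response".
- The Data analyses part of the abstract adds "Clinical outcomes and resource use following the initiation of Zinforo® treatment will be assessed according to" response time, in three groups: under 72 hours, over 72 hours, and no response. It then says that "median times to an outcome of interest (eg, length of stay in the hospital measured in days) will be calculated in each patient subgroup".
- Section 9.3 also lists total hospitalization and ICU durations separately, under hospitalization information.
- Section 9.7 allows the SAP to change the planned analyses.

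**SAP.**
- Section 5.1.8 lists "Duration of index hospitalization" and "Duration in intensive care unit during index hospitalization". It has no hospital-day or ICU-day item counted from the first dose.
- Shells 8 and 10 (CAP) and 35 and 37 (cSSTI) carry only those two durations. Tables 10 and 37 split them by responder and non-responder. (These are the numbers printed on the shells; the SAP's list of tables numbers the two cSSTI tables 37 and 39.)
- Section 7.1.4 says "Healthcare resource utilization will be described for patients hospitalized for CAP or cSSTI after starting Zinforo® and stratified by clinical response", using the 5.1.8 endpoints.

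**The concern.** The protocol treats whole-admission stay and stay after the first dose as two variables. The SAP carries forward only the first, although the objective it repeats concerns the period after Zinforo starts.

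The protocol expects some second-line and salvage use, so some patients may have spent days in hospital on other antibiotics before Zinforo. Those days enter every duration in Tables 8, 10, 35 and 37. If responders and non-responders waited different times for their first dose, the contrast in Tables 10 and 37 partly reflects care given before Zinforo. What is at stake is a quantity defined in the protocol that would not be reported, and a descriptive comparison that could be misread as describing the period on and after the drug.

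**Working it through.** The plan gives no figure to reproduce. The check compares the time origins and then asks what the planned tables allow a reader to recover.

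**1. Time origin, side by side**

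| Source | Hospital and ICU days counted from |
|---|---|
| Protocol 9.3, resource-use item | first Zinforo dose |
| Protocol abstract, Variables | first Zinforo dose |
| Objective 6 (Protocol 8, SAP 2.1.4) | after starting Zinforo; names neither days nor a dose date |
| SAP 5.1.8; Tables 8, 10, 35, 37 | whole index admission |

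The SAP does apply the post-dose window to one in-hospital item: renal replacement in 5.1.8 and Tables 14 and 41.

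**2. Identity per patient**

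Let S be the index stay, L the interval from admission to first dose, and P the stay from first dose to discharge or death. Then S = L + P, so S - P = L. I assume L is 0 days or more, meaning that Zinforo was started during the index admission.

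**3. Effect on the overall mean**

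Mean S - mean P = mean L. Assumed mean lags of 0, 1 and 3 days give overstatements of 0, 1 and 3 days.

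**4. Effect on the responder contrast**

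The contrast (non-responders minus responders) in S differs from the contrast in P by mean L(non-responders) - mean L(responders). If each group's mean lag is assumed to lie between 0 and 3 days, the shift runs from 0 - 3 = -3 to 3 - 0 = +3 days.

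**5. What the planned tables allow**

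The lag appears in Table 19 (CAP) and Table 46 (cSSTI; 48 in the list of tables), for all patients only.
- *Overall mean post-dose stay:* recoverable as mean S - mean L, apart from patients whose lag is unknown.
- *By response:* not recoverable. With two equal groups (assumed), mean lags of 0 and 3 days and mean lags of 3 and 0 days both average (0 + 3)/2 = 1.5 days overall, yet they shift the contrast by 3 days in opposite directions.
- *Medians:* not recoverable. In an invented example, stays of 6, 8 and 14 days with lags of 0, 3 and 1 give post-dose stays of 6, 5 and 13. Means: 28/3 - 4/3 = 9.33 - 1.33 = 8.00, which is correct. Medians: 8 - 1 = 7, but the true post-dose median is 6.
- *ICU days:* not recoverable. No interval from ICU admission to first dose is tabulated.

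**6. Whether the missing quantity can be derived**

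For hospital stay, yes: Protocol 9.3 collects both total duration and the interval from admission to first dose. For ICU time it is uncertain: the abstract lists an ICU discharge date, while Protocol 9.3 and SAP 5.1.8 list ICU duration without dates.

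**The case against.** The strongest reply is that little is lost. The study is descriptive, whole-admission stay is itself a protocol variable, the lag is collected, and post-dose stay can be derived per patient at any time. Protocol 9.7 also permits the SAP to depart from the plan and requires an amendment only for major changes to primary endpoints. All of this is true and it lowers the severity. It does not close the gap: the SAP keeps Objective 6 and nowhere says that the window has changed.

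Several stronger readings are tempting, and the documents do not support them.
- A reader might infer that Objective 6 itself sets the first dose as day zero for hospital and ICU days. It does not; that clock is explicit only in Protocol 9.3 and the abstract.
- A reader might infer that SAP 7.1.4 mislabels the results. Its wording is ambiguous: the phrase about starting Zinforo can describe the patients, as the heading of 5.1.8 does. The shell titles state openly that they cover the index hospitalization.
- A reader might take the abstract's length-of-stay sentence as post-dose stay. That sentence names no start point; only the sentence before it gives the window.
- A reader might take the lag as certainly non-negative. The phrase in 5.1.8 about the index hospitalization can be attached to the resource use rather than to the start of Zinforo, and Tables 19 and 46 allow home and outpatient administration.
- A reader might extend the point to the cost tables. SAP 5.1.8 does not say which bed days count, but that is a separate missing detail, and no objective includes cost.

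**Conclusion.** The post-dose hospital and ICU durations defined in Protocol 9.3 and the abstract are absent from the SAP endpoints and shells. Reporting whole-admission stay is not an error; omitting the post-dose measure is. As planned, the tables yield at most an approximate overall mean post-dose stay, with no by-response value, no median and nothing for ICU time.

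The size and direction of any effect are unknown. The 0, 1 and 3 days, and the -3 to +3 days for the contrast, follow directly from assumed lags and are not evidence that a shift exists. They also rest on the assumption that Zinforo was started during the index admission. If the lag does not differ by response, the mean contrast is unaffected.

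No hypothesis test is involved and the gap can be closed from data already planned for collection. Severity is minor to should-fix.

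**What to change.** 1. In SAP 5.1.8, define post-dose stay as index duration minus the interval from admission to first dose. Add it as a row in shells 8, 10, 35 and 37, overall and by response, with mean (SD), median (min-max) and number missing. Keep whole-admission stay as a separately labelled row.
2. Report post-dose ICU days only if the CRF holds ICU dates. Otherwise state in SAP 7.1.4 that ICU days and other items without timing cover the whole index admission, which also settles the ambiguity there.
3. Note that Tables 10 and 37 give a responder/non-responder split. The abstract's three response-time groups would need additional columns.

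A cheaper alternative is to declare in the SAP, as Protocol 9.7 allows, that Objective 6 is reported over the whole admission. That removes the inconsistency but leaves the protocol's post-dose variable unreported, so item 1 is preferable.

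The cost is one derived variable, one row in each of four shells, and a sentence in 7.1.4. The downside is that post-dose stay will be missing wherever the lag is unknown, and ICU time may have to stay whole-admission.
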